For each out-of-range laboratory result, the Investigator or designee will enter directly in the eCRF the Investigator judgment on the presence or the absence of a clinical significance.

All clinically significant out-of-range laboratory values for blood and/or urine samples collected at screening will be recorded in the medical history (report a diagnosis rather than an individual laboratory parameter abnormality whenever possible).

All clinically significant out-of-range laboratory values for blood and/or urine samples collected after screening, are to be reported as an AE if this abnormality was not present at the screening visit or is assessed as having worsened since the screening visit (i.e., there is a significant change from screening).

If the Investigator observes a clinically relevant laboratory test value, the laboratory tests will be repeated as soon as possible and monitored until the values have returned to normal and/or an adequate explanation for the abnormality is found. This does not apply to screening laboratory test values, except for TB test and CPK, which will be assessed at Screening 1 visit, and for which one retest is allowed at the Screening 2 visit (see [Table 2](#)).

In instances when a laboratory abnormality is reported as an AE or AESI, whenever possible, the Investigator is to provide a diagnosis rather than reporting individual laboratory abnormalities.

The following out-of-range laboratory values should be reported as an AESI (see Section [7.2.4.2.1](#)):

- Elevated ALT or AST (>3 ULN) in combination with elevated bilirubin (>2 ULN), whether or not considered as related to the study drug by the investigator;
- Elevated CPK (≥ 2.5 ULN) if considered as related to the study drug by the investigator.

A summary of sample volumes and the number of blood samples is detailed in [Appendix 1](#).

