**Analysis Visit**

Study day is relative to date of randomization. Day -1 is the day before randomization, and day 1 is date of randomization.

Assessments at early termination and unscheduled visits will be slotted based on the following visit window.

Period	Analysis Visit	Target day (relative to randomization)	Day ranges
Screening Period	Screening 1	-28	-28 to -8
	Screening 2	-7	-7 to -1
Treatment	Baseline	1	≤1
	Week 1	8	2-11
	Week 2	15	12-22
	Week 4	29	23-43
	Week 8	57	44-71
	Week 12	85	72-99
Follow-up	Week 16	113	100-119
	Week 18	126	>119

The diary reported during study will be classified into analysis visits as follows (i.e., during the 7 days prior to the target day of analysis visit. In this case, the target day of analysis visit is relative to date of the first planned study drug.):

- Day -7 to -1 = Baseline
- Day 1 to 7 = Week 1
- Day 8 to 14 = Week 2
- Day 22 to 28 = Week 4
- Day 50 to 56 = Week 8
- Day 78 to 84 = Week 12
- Day 106 to 112 = Week 16
- Day 120 to 126 = Week 18

These analysis visits will be used in the calculations for all week-based parameters collected on subject's diary (e.g., pruritus NRS, VRS, Sleep disturbance NRS, PAS, DPS, DLQI) Other non-diary data, such as , IGA, vital signs, body weight, clinical laboratory assessments, respiratory assessment/PEF, will be analyzed according to actual scheduled visits.

For efficacy and safety data (except clinical laboratory assessments), where two or more assessments (include both scheduled and unscheduled assessments) are available for the same visit interval, the one closest to the target visit date will be used for the summary and analyses. For clinical laboratory assessments, if repeated measurements are taken for either time point (scheduled visit), then the last measurement will be used for the value for that time point. Unscheduled labs will be included in listings, but not summaries of the data. All post baseline assessments, including repeated or unscheduled visits, will be used for potentially clinically significant value (PCSV) determinations.

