#### **5.8.4 Clinical Laboratory Evaluation**

All laboratory values will be reported in SI units.

Laboratory data (absolute values and change from baseline) will be summarized descriptively by visit and treatment group.

In addition, the number and percent of subjects below, within, and above the laboratory reference ranges and the number and percentage of subjects who met criteria of PCSV (see Appendix 5) will be summarized by treatment group. Shift tables will be generated using the reference ranges. The shift will also be illustrated by the spaghetti plots.

A by-subject listing of all laboratory data will be provided by treatment group, with abnormal values flagged. Laboratory reference ranges should also be listed.

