Bilirubin total	µmol/L	mg/dL	>2.0 ULN and Baseline ≤2.0 ULN
CPK	U/L		>3.0 ULN and Baseline ≤3.0 ULN
Fibrinogen	g/L	mg/dL	Not provided
GGT	U/L		>2.5 ULN and Baseline ≤2.5 ULN
Albumin	g/L	g/dL	≤30 g/L and Baseline >30g/L
Uric acid *Male16-59			>600 µmol/L and ≤600 µmol/L at Baseline for Male;
*Female>16	mmol/L	mg/dL	>500 µmol/L and ≤500 µmol/L at Baseline for Female
*Male >60			
Cholesterol total	mmol/L	mg/dL	>10.34 mmol/L and ≤10.34 mmol/L at Baseline
Triglycerides	mmol/L	mg/dL	>5.7 mmol/L and ≤5.7 mmol/L at Baseline

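### The last-value rule for repeated laboratory tests can drop the abnormal result that triggered the repeat from visit summaries and shift tables

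*SAP*

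**What the plan says.** SAP 5.2, under Analysis Visit, sets one rule for most efficacy and safety data (take the assessment closest to the target day) and a separate rule for laboratory data: "if repeated measurements are taken for either time point (scheduled visit), then the last measurement will be used" as that visit's value. Two sentences follow. The first is "Unscheduled labs will be included in listings, but not summaries of the data". The second is "All post baseline assessments, including repeated or unscheduled visits, will be used for potentially clinically significant value (PCSV) determinations".

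Protocol 7.2.3 gives the trigger for a repeat: "If the Investigator observes a clinically relevant laboratory test value, the laboratory tests will be repeated as soon as possible". Monitoring then goes on until the value is normal, or the abnormality is adequately explained, or both. Screening values are exempt, apart from one retest of the TB test and of CPK.

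SAP 5.8.4 uses the visit values for descriptive summaries of values and changes from baseline, and for counts of subjects by position relative to the reference range. It also states: "Shift tables will be generated using the reference ranges". PCSV counts and a listing of all laboratory data with abnormal values flagged complete the laboratory outputs.

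**The concern.** The repeats are selected on outcome. The only post-screening trigger that Protocol 7.2.3 names for these blood and urine tests is a clinically relevant result. An unremarkable result has no counterpart repeat that could turn it abnormal. If the last value stands for the visit, replacement runs mostly one way, from abnormal toward normal.

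The affected outputs are descriptive, but they are the standard view of laboratory safety by arm. The visit descriptions in Protocol 8.1.2 place post-baseline hematology and full biochemistry at Week 4 and Week 12, so one replaced visit value can be half of a subject's planned tabulated evidence. CPK is a live question for this drug: Protocol 1.2 lists increased CPK among the adverse events seen in at least 5% of nemolizumab-treated patients in the phase 2a atopic dermatitis study.

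**Working it through.** The documents give no figure on this point, so the check is mainly of how the rules combine.

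**Step 1. What happens to the triggering value.**

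| Class of the repeat | Repeat result | Value tabulated at the visit | Effect on range counts and shifts |
|---|---|---|---|
| Repeat of the scheduled visit | Back in range | Repeat | Abnormality drops out |
| Repeat of the scheduled visit | Still out of range | Repeat | None, though the mean may move |
| Unscheduled | Any | Original planned sample | None |

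**Step 2. Is the class defined?** No. A retest ordered after a result has been read will usually be a later draw, and Protocol 8.1.4 provides hematology and biochemistry at unscheduled visits. That points to the unscheduled class. But SAP 5.2 also slots unscheduled assessments into windows, and Week 4 covers Days 23 to 43, so a retest up to 43 − 29 = 14 days after the target day falls inside it. The same section says that laboratory data follow the actual scheduled visits. Nothing says when a retest is a repeated measurement and when it is an unscheduled one.

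**Step 3. What keeps the abnormal value elsewhere.**

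- PCSV counts use every post-baseline value.
- Under Protocol 7.2.3, clinically significant values that are new or worse since screening are adverse events. SAP 5.8.2 and 5.8.3 tabulate these and the adverse events of special interest (AESIs).
- For liver enzymes, the AESI limits (ALT or AST above 3 ULN with bilirubin above 2 ULN) equal the PCSV limits in SAP Appendix 5, so there is no threshold gap.
- For CPK, the PCSV rule is ">3.0 ULN and Baseline ≤3.0 ULN". The AESI starts at 2.5 ULN, but only if the investigator judges the rise related. A rise from 2.5 up to 3.0 ULN judged unrelated meets neither definition, and nor does any out-of-range value below 2.5 ULN.
- For fibrinogen, Appendix 5 gives no PCSV limit. LDH and hsCRP are not in the table. For these analytes the range counts and shift tables are the main tabulated laboratory evidence.

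**Step 4. Illustration of size, on assumed rates.** Let p be the true out-of-range rate at a visit, a the share of abnormal values that are repeated and attributed to that visit, and s the share of those repeats back in range. The tabulated rate is p × (1 − a × s). Only the 35 subjects per group come from the documents. The assumed p is 20% on nemolizumab and 10% on placebo, that is 7.0 and 3.5 subjects and a difference of 10 points. The shares a and s are assumed equal in both arms.

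| a | s | 1 − a × s | Nemolizumab | Placebo | Difference (points) |
|---|---|---|---|---|---|
| 0 | any | 1 | 7.0 | 3.5 | 10.0 |
| 0.25 | 0.5 | 0.875 | 6.1 | 3.1 | 8.8 |
| 0.25 | 0.8 | 0.80 | 5.6 | 2.8 | 8.0 |
| 0.5 | 0.5 | 0.75 | 5.25 | 2.6 | 7.5 |
| 0.5 | 0.8 | 0.60 | 4.2 | 2.1 | 6.0 |
| 1 | 0.5 | 0.50 | 3.5 | 1.75 | 5.0 |
| 1 | 0.8 | 0.20 | 1.4 | 0.7 | 2.0 |

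The share of abnormalities lost is a × s. It is zero at a = 0 or s = 0, 12.5% to 20% at a = 0.25, and 50% to 80% at a = 1. The last case is an upper bound: it needs every out-of-range value to be repeated, whereas the protocol repeats only those judged clinically relevant.

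**The case against.** The strongest reply is that the rules will seldom meet. A retest normally needs a new visit, such visits are unscheduled, and the SAP keeps unscheduled laboratory values out of the summaries. This stands as a limit on frequency. It does not remove the rule, because the SAP plainly expects some repeats to count under a scheduled visit and leaves the boundary open.

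A second reply is that the signal is caught elsewhere. Protocol 7.2.3 counts a value as clinically significant if it calls for closer follow-up, so a value that prompts a repeat would ordinarily become an adverse event when new or worsened. This also stands in large part, and it confines the gap to the analytes and CPK range in Step 3.

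Third, the endpoint of monitoring is not normality alone, so the last value may still be abnormal. A redraw of a whole panel could also replace normal values of other analytes. Both points stand, which is why the direction is general rather than certain.

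Fourth, the repeat rule is read from Protocol V00 of 30 May 2017, while the SAP is written against Amendment 2.0 of 09 April 2018. Laboratory text did change between them: SAP Appendix 1 limits the Week 8 CPK sample to France, a note absent from V00. Whether section 7.2.3 changed cannot be seen.

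**Conclusion.** The point holds in conditional form. As written, the SAP rule can selectively remove abnormal results from visit summaries, range counts and shift tables, when a repeat is attributed to the scheduled visit and has returned to range. The size cannot be derived from the documents. It depends on how repeats are classed and how many normalise, and on section 7.2.3 being unchanged in Amendment 2.0.

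A reader might go further and infer that these tables will in fact show normalised values, that a CPK or liver-enzyme signal would be hidden, or that the comparison between arms is biased by a known amount. The documents do not support this. Unscheduled repeats replace nothing, PCSV counts and adverse event tables retain the value, and the liver limits coincide. The difference between arms shrinks by a × s only if repeat and recovery rates are equal in both arms. Nor is it an error in itself that laboratory data have a different rule from other safety data.

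The change should be made for the descriptive safety outputs. No efficacy result is touched.

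**What to change.** In SAP 5.2:

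- For post-baseline by-visit laboratory summaries, range counts and visit shift tables, use the first valid planned sample at the scheduled visit. Let a repeat replace it only when the original sample is invalid, for example haemolysed.
- Define when a retest is a repeat of a scheduled visit and when it is unscheduled, and state that window slotting does not bring retests into the by-visit laboratory summaries.
- Keep the existing rule of the last pre-dose value for baseline.

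In SAP 5.8.4, add a shift table from baseline to the worst post-baseline value, using scheduled, repeat and unscheduled results.

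The cost is a short text edit and one extra table, with no new data. Abnormality counts may come out slightly higher.

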### 5.3 Study Subjects

#### 5.3.1 Disposition of Subjects

A clear accounting of the disposition of all subjects who enter the study will be provided, from screening to study completion.

The following subject disposition summaries will be produced:

- The number of subjects screened (Analysis population: Screened Subjects)
- Screen failures (Analysis population: Screened Subjects)
- Subjects Randomized by clinical site and overall (Analysis population: All Randomized Subjects)

The following summaries will be produced for ITT population:

- The number of subjects randomized
- The number and percentage of subjects treated (with at least one dose of study drug)
- The number and percentage of subjects randomized but not treated (not taken any dose of study drug)
- The number and percentage of subjects who temporarily discontinued the study treatment and reasons for discontinuation
- The number and percentage of subjects who permanently discontinued the study treatment and reasons for discontinuation
- The number of subjects who completed study treatment period (defined as completing week 12 visit)
- The number of subjects who completed the study
- The number of subjects who discontinued from the study and reason of discontinuation
- A Kaplan-Meier plot of the time to permanent study treatment discontinuation will be provided. Subjects who did not discontinue from the study treatment will be censored at their last dose of study drug (Analysis population: ITT).
- A Kaplan-Meier plot of the time to study discontinuation will be provided. Subjects who did not discontinue from the study will be censored at the date of study completion or the last visit date on the study (Analysis population: ITT).

- Time (days) to permanent discontinuation of study treatment by reasons for discontinuation will be displayed graphically in subjects having permanently discontinued study treatment.
- Time (days) to study discontinuation by reasons for discontinuation from study will be displayed graphically in subjects having discontinued study.

By-subject listings of eligibility details, randomization details, visit dates and withdrawal/study completion details (including reason for discontinuation and duration of treatment prior to discontinuation) will be provided.

### 5.3.2 Protocol Deviations

Deviations from the protocol including violations of inclusion/exclusion criteria will be assessed as ‘minor’ or ‘major’. Major PDs are defined as those deviations from the protocol that are likely to have an impact on the subject’s right, safety, well-being, and/or the validity of the data for analysis. Minor deviations include all deviations from the protocol excluding those considered as major. The impact of major protocol deviations on the efficacy and/or safety results will be investigated by assessing the robustness of the study results and conclusions to the choice of analysis population (see Section 5.4), both including and excluding data potentially affected by major protocol deviations. Major PDs that will lead to the exclusion of a subject from the per-protocol (PP) population will be identified. The final determination of major protocol deviations and the exclusion of subjects from each of the analysis populations will be made prior to database lock.

Refer to the study protocol deviation specification for more information.

The following protocol deviation summaries will be provided:

- Number and percentage of subjects with a major protocol deviation by type of deviation (Analysis population: ITT)
- Number and percentage of subjects with a major protocol deviation resulting in exclusion of subjects from PP analysis by type of deviation (Analysis population: ITT)

A by-subject listing of protocol deviations will be provided.

## 5.4 Analysis Populations

The following analysis populations will be used to analyze the data.

**Intent-to-Treat Population (ITT):**

The ITT population will consist of all randomized subjects.

**Per Protocol Population (PP):**

The PP Population is defined as comprising the ITT subjects who have no major protocol deviations that would have a significant effect on the efficacy of the study treatment.

The PP population will be finalized prior to the final database lock.

**Safety Population (SAF):**

The safety (SAF) population will comprise all subjects in ITT population who receive at least one dose of study drug.

**PK Analysis Population (PKAP):**

The PK analysis population will include all subjects in the SAF population who provide at least one post-baseline evaluable drug concentration value.

**PD Analysis Population (PDAP):**

The PD statistical analyses will be performed based on the PP population, and after exclusion of samples unable to produce reliable quantifications of cytokines, and/or immunohistological markers and/ or transcriptomic biomarkers, due to the material quantity and/or quality.

The efficacy summaries and analyses will be based on the ITT population, which is based upon the Intention-to-Treat (ITT) principle. In the event that a subject is allocated the incorrect study treatment as per the study randomization list, subjects will be summarized and analyzed 'as randomized' (i.e., by randomized treatment group). In the event that a subject is stratified incorrectly, 'randomized stratum' will be used rather than 'actual stratum'.

For the primary and selected secondary efficacy endpoints, a sensitivity analysis will be performed on the PP population to assess the robustness of the study conclusions to the choice of analysis population. Subjects will be included in the analysis according to the treatment 'as randomized'.

The safety summaries and analyses will be based on the SAF population. Randomized subjects will only be excluded if there is clear, documented evidence that the subject did not receive any study drug injection. In the event that a subject is allocated the incorrect study treatment as per the study randomization list, subjects will be summarized and analyzed 'as treated' (i.e., by allocated treatment group).

Upon database release, protocol deviation and analysis population outputs will be produced and will be reviewed by Sponsor. An analysis population classification meeting will be arranged to discuss the outputs and to decide which subjects and/or subject data will be excluded from certain analyses. Decisions made regarding the exclusion of subjects and/or subject data from analyses will be made prior to database lock and unblinding and will be documented and approved by Sponsor.

The following analysis population summaries will be provided:

- The number and percentage of subjects in each study population will be presented by study treatment group including total (Analysis population: ITT).

A by-subject listing of analysis population details will be provided. This listing will be presented by treatment group and will include: subject identifier, inclusion/exclusion flag for each population and reason for exclusion from each population. All randomized subjects will appear on this listing.

The following derived and computed variables will be produced:

Variable Description	Computation Methods, Notes, or Equation(s)
Flag of ITT subjects	'Y' if subjects randomized into the study; otherwise 'N'
Flag of SAF subjects	'Y' if subjects in ITT and date and/or time of the first dose injection on Study Drug Administration form is non-missing; otherwise 'N'
Flag of PP subjects	'Y' if subjects in ITT who complete 12-week Treatment Period with the exception of major protocol violators who have significant effect on the efficacy; otherwise 'N'
Flag of PKAP subjects	'Y' if subjects in the safety population who provided at least one post-baseline evaluable drug concentration value; otherwise 'N'
Flag of PDAP subjects	'Y' if subjects in the PP, and after exclusion of samples unable to produce reliable quantifications of cytokines, and/or immunohistological markers and/ or transcriptomic biomarkers, due to the material quantity and/or quality; otherwise 'N'

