9.2.1 Data transformations

9.2.2 Populations analyzed, evaliability and limitation / evaluation of bias

The statistical analyses will be performed based on the following subject populations.

9.2.2.1 *Intent-to-treat (ITT) Efficacy Population*

The ITT Population is defined as comprising all subjects who are randomized. All primary efficacy variables and secondary efficacy variables will be analyzed based on the ITT Population.

9.2.2.2 *Per-protocol (PP) Efficacy Population*

The PP Population is defined as comprising the ITT subjects who have no major protocol deviations. This will be the primary population for this study.

Major deviations are categorized into 4 categories:

- 1) Entrance criteria deviations,
- 2) Non compliance,
- 3) Concomitant therapies taken during the study, interfering with efficacy,
- 4) Administrative errors such as unblinding or study drug dispensing errors.

PP analysis will be conducted only up to Week 4.

9.2.2.3 *Safety Population*

The Safety Population is defined as comprising the ITT Population subjects who receive the study drug at least once. Randomized subjects will only be excluded if there is a clear documented evidence that the subject did not receive any study drug injection. All safety data will be summarized based on the Safety Population.

9.2.2.4 *PK analysis population*

The PK analysis population will include all subjects in the safety population who provide at least one post-baseline evaluable drug concentration value.

9.2.2.5 *PD analysis population*

The PD statistical analyses will be performed based on the PP population, and after exclusion of samples unable to produce reliable quantifications of cytokines, and/or immunohistological markers and/ or transcriptomic biomarkers, due to the material quantity and/or quality.

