### 5.7 Efficacy Evaluation

Primary inference for efficacy analysis will be the percent change from baseline in NRS to week 4 (weekly average of the peak). This analysis will be based on the ITT population, and repeated using the PP population. Primary imputation method for any missing data including those who took rescue medication as failure will be the LOCF (last observation carried forward) approach. In addition, Multiple Imputation (MI) using the missing at random assumption will be conducted on ITT population:

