## 5.10 Determination of Sample Size

For the current study, it is assumed that the common standard deviation is 35 and that the true difference between Nemolizumab and the placebo is 30% in terms of percent change from baseline in worst itching score on a NRS at Week 4.

With an effect size of  $(30/35=) 0.857$ , a power of 90% and a type I error of 5% two-sided; at least 30 subjects are needed per group. In order to maintain the power of the tests, for per-protocol population, in case of drop outs/major deviations at Week 4, the sample size will be increased to 35 subjects per group, i.e. 70 to be randomized.

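### SAP 5.4 defines the per-protocol population in two ways; the flag version drops subjects from the Week 4 analysis for leaving the study after Week 4

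*SAP*

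**What the plan says.** SAP 5.4 defines the PP population twice.

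- **In words** (Per Protocol Population): "The PP Population is defined as comprising the ITT subjects who have no major protocol deviations that would have a significant effect". What counts is whether efficacy is affected; completing any period is not required.
- **As a flag** (table of derived variables, same section): the value is Y for "subjects in ITT who complete 12-week Treatment Period with the exception of major protocol violators who have significant effect on the efficacy". Everyone else gets N.

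The only definition the SAP gives of completing the treatment period is in the disposition list of 5.3.1: "The number of subjects who completed study treatment period (defined as completing week 12 visit").

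The primary endpoint is at Week 4, and its diary window is "Day 22 to 28 = Week 4" (SAP 5.2, Analysis Visit). On the primary analysis, SAP 5.7 says: "This analysis will be based on the ITT population, and repeated using the PP population". SAP 5.4 gives the purpose of PP, which covers the primary endpoint and some secondary ones: "a sensitivity analysis will be performed on the PP population to assess the robustness of the study conclusions".

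The sizing text in SAP 5.10 raises the sample from 30 to 35 per group "for per-protocol population, in case of drop outs/major deviations at Week 4". Protocol V00, section 9.2.2.2, has no completion condition and states: "PP analysis will be conducted only up to Week 4". The SAP is written to protocol Amendment 2.0, which was not among the documents supplied, so it is not known whether that limit still applies.

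**The concern.** Under the flag, entry to a Week 4 analysis depends on something that happens up to eight weeks after the endpoint was measured. Leaving the study is not in itself a major deviation, so the flag mixes two different exclusions. A PP result that differs from ITT might reflect deviations, later withdrawal, or both, and the comparison loses its stated purpose as a check on the choice of population.

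Later withdrawal may also be related to the Week 4 result, since protocol 5.8 lists lack of efficacy among the reasons for leaving. If that relation, or the amount of loss, differs between arms, the Week 4 PP difference is biased in a direction that cannot be known in advance. The PP sample may also fall below the 30 per arm in SAP 5.10, because that allowance covers losses at Week 4 only. The PD population is built from PP and inherits the ambiguity.

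**Working it through.** **1. The two rules applied to one subject.** Take a randomized subject with no major deviation and enough diary entries on Days 22–28 who withdraws at Week 6.

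| Rule | Week 12 visit needed? | PP status |
|---|---|---|
| SAP 5.4, definition in words | No | Y |
| SAP 5.4, derived flag | Yes (through 5.3.1) | N |
| Protocol V00 9.2.2.2 | No | Y |

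A subject who stops study drug but stays in the study is not affected: protocol 6.5 asks such subjects to attend all remaining visits, so they can still complete Week 12. The conflict concerns those who leave the study or miss that visit. It needs no arithmetic.

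**2. The plan's own sample size.** Inputs from SAP 5.10: difference 30, SD 35, two-sided 5%, power 90%. The effect size is 30/35 = 0.857. A two-sample t-test (noncentral t) needs 30 per arm, with power 90.4%; the normal approximation gives 29. The stated 30 is reproduced. The allowance is 5/35 = 14.3% per arm.

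**3. PP power as subjects are lost.** Noncentral t with n1 + n2 − 2 degrees of freedom and noncentrality (30/35)/√(1/n1 + 1/n2). The documents give no loss rate between Week 4 and Week 12, so every rate below is an assumption.

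| Total loss from 35 per arm | Left per arm | Power |
|---|---|---|
| 0% | 35 | 94.2% |
| 5% | 33.25 | 93.1% |
| 10% | 31.5 | 91.7% |
| 14.3% (5 lost) | 30 | 90.4% |
| 17.1% (6 lost) | 29 | 89.4% |

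Unequal loss, placebo/active:

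| Loss | From 35 per arm | From 30 per arm (Week 4 allowance used up) |
|---|---|---|
| 20%/10% | 28/31.5: 90.1% | 24/27: 85.0% |
| 30%/10% | 24.5/31.5: 87.8% | 21/27: 82.2% |
| 30%/20% | 24.5/28: 86.0% | 21/24: 80.1% |

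**4. Selection, as an illustration of mechanism and not an estimate of size.** Let z be the Week 4 result in within-arm SD units, with higher values worse, and let logit P(leave) = a + b·z, with a solved to give the stated loss. The PP difference is 30 + 35 × (mean z among placebo subjects retained − mean z among active subjects retained). For 20%/10% loss and b = 0.5, the retained means are −0.0962 and −0.0488, giving 30 + 35 × (−0.0474) = 28.34.

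| Loss (placebo/active), same b in both arms | b = 0.5 | b = 1.0 |
|---|---|---|
| Equal loss (5/5, 10/10, 20/20) | 30.00 | 30.00 |
| 10%/5% | 29.15 | 28.47 |
| 20%/10% | 28.34 | 27.11 |
| 30%/20% | 28.37 | 27.21 |
| 30%/10% | 26.71 | 24.33 |

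| Only active-arm leaving tracks poor response; active loss | b = 0.5 | b = 1.0 |
|---|---|---|
| 5% | 30.86 | 31.65 |
| 10% | 31.71 | 33.18 |
| 20% | 33.37 | 36.06 |

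With b = 0 the difference stays at 30 whatever the loss.

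**The case against.** Several points on the other side have force.

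- **The definition in words has no time limit either.** A qualifying deviation at Week 10 would also remove a subject from the Week 4 PP analysis. This stands: the completion condition widens an existing weakness, and the fix has to add a time limit as well as delete the condition.
- **The stakes are limited.** The SAP rests efficacy inference on ITT, and PP is a sensitivity analysis beside LOCF, observed-case and multiple-imputation analyses. This stands too. A supporting analysis does not need 90% power, so the power figures are secondary.
- **The loss rates are assumed.** With SD 35 and 30 per arm, the standard error of the difference is 35 × √(2/30) = 9.04. The largest illustrated shift, 36.06 − 30 = 6.06, is smaller than that, and at 10%/5% loss the shift is 0.85 to 1.53. Protocol 5.7 and 6.5 also favour retention. The figures show that bias can arise in either direction, not that it will be large.
- **A 12-week horizon may be intended.** SAP 5.7.2 plots PP results over time, and the PD population uses PP. That could justify a later horizon for later displays; it does not justify a Week 12 condition on a Week 4 analysis.
- **Exclusions are settled before lock and unblinding** (SAP 5.3.2 and the classification meeting in 5.4) and are listed with reasons. This limits result-driven choice and makes exclusions visible, but the meeting would have two written rules and nothing to choose between them.

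The missing Amendment 2.0 bears only on the comparison with the protocol. The contradiction lies within the SAP.

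**Conclusion.** The concern holds and should be fixed. The two PP rules in SAP 5.4 give different answers for the same subject, and nothing in the SAP ranks them. That conclusion rests on the text alone.

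The main harm is to interpretation: under the flag, the Week 4 PP analysis no longer isolates the effect of protocol deviations. The numerical consequences depend on assumptions. With equal loss, PP power stays at or above 90% up to 5 lost per arm, drops to 89.4% at 6, and reaches 80.1% only if 30%/20% later loss comes on top of the full Week 4 allowance. Bias in the PP difference is zero under non-informative leaving, or under equal loss and equal dependence on response; in the other cases shown, a true 30 becomes 24.33 to 36.06. The primary ITT result is not touched.

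**What to change.** Delete the 12-week completion condition from the PP flag and make the definition in words and the flag identical, with a time limit tied to the primary endpoint. Suggested flag for Week 4: Y if the subject is in ITT and has no major protocol deviation, up to and including the Week 4 assessment, that would materially affect efficacy; otherwise N.

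If the protocol version in force allows PP displays or PP-based PD analyses after Week 4, judge PP status for each up to its own visit and align the PD population text and flag. If it does not, keep PP to Week 4, as protocol V00 states.

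The cost is SAP wording in two places of section 5.4 before database lock, plus the PD entries and some visit-specific flags if later PP analyses are kept. It needs no additional patients and no new data.
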